3. STUDY DESIGN

The proposed project concerns a monocentric, prospective, double-blind, randomized, placebo-controlled interventional trial with a (1:1) parallel design. The study will be conducted over a total duration of 2 years, encompassing recruitment, intervention, and singular measurements, all carried out at the NUTRIM Clinical Research Unit (CRU) at Maastricht University.

Visit 1

Recruitment procedures are outlined in paragraph 11.2 and are in accordance with the study “taVNS and acute stress response” (NL87188.068.24/METC 24-029), which has received ethical approval. Interested study participants will receive a verbal explanation of the study over the phone and will be sent a comprehensive electronic information letter. At least 7 days later, they will be invited to attend an inclusion visit at Maastricht University. During this visit, participants will undergo eligibility screening and receive detailed instructions regarding the study procedures. Eligible participants will be asked to provide written informed consent before proceeding. Subsequently, eligible participants will be asked to complete several (digital) questionnaires, including a baseline characteristics questionnaire, the Generalized Anxiety Disorder 7-Item Scale (GAD-7), the Patient Health Questionnaire-9 (PHQ-9), and the Big Five Inventory (BFI). All information obtained during the screening visit, including participant data and study-related details, will be securely recorded using Castor, an electronic data capture system. After this screening visit participants will be randomized in a 1:1 parallel design by an investigator to receive either taVNS or sham stimulation on the second test day, with appropriate blinding procedures in place.

Visit 2

A second visit, which serves as the test day, will be scheduled. During this visit, participants will receive either taVNS or sham stimulation, administered immediately after nausea induction, based on their randomization.

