The stimulation parameters comprise a biphasic rectangular pulse wave with an impulse frequency of 25Hz, impulse duration of 30 seconds, impulse pause of 30 seconds, and pulse width of 450ms. These parameters have been identified as the most optimal treatment frequencies for taVNS based on systematic reviews (27, 28). Active stimulation will be programmed to deliver only subthreshold stimuli. The device will blink when stimulation is delivered. In the sham (control) group, the electrode will be non-conducting, but the device will still blink to maintain blinding (28). The electrodes used in the tVNS and sham groups differ slightly. Consequently, the investigator responsible for programming the devices will be aware of the treatment allocation, while participants will remain blinded. To ensure double blinding, the randomization code will be altered prior to data analysis, ensuring that the investigator conducting the analysis will be blinded to the treatment allocation. The randomization code will be kept confidential until after the modified intention-to-treat analysis has been reported.

During the stimulation phase, nausea severity will be assessed using a 0-100 VAS score, where 0 indicates “no nausea” and 100 represents the “worst nausea imaginable”. VAS scores will be recorded every 5 minutes, continuing for 30 minutes post-stimulation to evaluate the efficacy of taVNS in alleviating nausea. Additionally, other gastrointestinal symptoms and the desire to eat will be measured at predetermined time points using VAS scores.

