5.1.2 Sham stimulation

In the control group, sham stimulation will be administered to the same electrode location (left cymba conchae) using an identical device as that used for taVNS. The electrode used for sham stimulation will be non-conducting, ensuring that there is no stimulation of the vagus nerve. Although the devices for tVNS and sham stimulation appear identical, the electrodes for each group are slightly different. Consequently, the investigator responsible for programming the devices will be aware of the treatment allocation. Participants will not be aware of the treatment received since stimulation is provided to the same location, and the device will still blink during both types of stimulation to maintain blinding (28). The randomization code will be altered

before analysis, ensuring that the investigator conducting the data analysis remains unaware of the treatment allocation. The randomization code will be kept confidential until after the modified intention-to-treat analysis has been reported.

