5.2 Use of co-intervention

5.2.1 Intragastric lipid infusion

As a co-intervention, an intragastric infusion of a 50% fat emulsion in water will be administered to induce nausea. A 10-F gauge single-lumen polyurethane nasogastric tube (Nutricair Enteral-Enfit, Charrière 10) will be manually inserted by the coordinating investigator, positioning the catheter in the stomach and connecting it to a nutrition enteral delivery pump (Applix Smart pomp). A 20/60ml Nutricair Enteral-Enfit syringe will be used to administer the fat emulsion through the feeding tube. Standard clinical protocols for nasogastric tube placement will be followed, including a pH measurement to verify the tube's position, ensuring participant's safety and comfort.

The fat emulsion (Calogen, NUTRICIA, Netherlands) used is comparable to that employed in previous research on intragastric nausea induction (1). It is a medical nutritional product typically used to address an 'energy deficit' in patients who are unable to meet their recommended energy intake through regular food and/or oral nutritional supplements. The emulsion is suitable for enteral use and can be administered via a nasogastric tube (31). See D6.1_SPC_Calogen_Versie1.0_dd 16-10-2024 & D6.2_Calogen_Voedingstabel_Versie1.0_dd 15-10-2024 for additional information.

The fat emulsion consists of 50% long-chain triglyceride and 50% water (osmolality: 0 mOsm/L, Calogen, NUTRICIA, Netherlands). Previous research has shown that long-chain triglycerides elicit a stronger nausea response than medium-chain triglycerides, which is why long-chain triglycerides were selected as the primary component (1). The infusion rate will be set at 5 ml/min (22.5 kcal/min) and will continue until the participant experiences nausea, indicated by a VAS score of 50/100 (1). Based on previous studies, it is expected that approximately 258 + 32 ml of the fat emulsion is required to induce nausea through gastric relaxation, with the process taking approximately 52 ± 6 minutes (1). If the nausea score does not reach the VAS of 50/100 after 1.5 hours of infusion, the infusion will be discontinued, and the test day will be terminated. In this case, the participant will be considered a drop-out due to non-response to the nausea-inducing stimulus.

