5.3 Escape medication

To ensure participant safety, an ondansetron dissolvable tablet will be administered as escape medication when nausea reaches a severity level of 80 or higher out of 100 on the VAS scale, indicating severe discomfort and an imminent vomiting sensation. Following the immediate termination of the lipid infusion, a single dose of 4 mg will be given, with a maximum of four doses (16mg total) allowed per day if necessary. Based on previous research using more intensive nausea induction methods, including intraduodenal lipid infusion and gastric distension, in which 2 out of 12 healthy participants experienced vomiting, we do not expect frequent vomiting in our study (10).

Ondansetron is a well-established anti-emetic that exerts its effects primarily through antagonism of 5HT₃ (serotonin) receptors. It is commonly used for the management of nausea in clinical settings (32). See D6.4_Ondansetron_SPC_Versie1.0_dd 22-07-2024 for additional information.

Given that participants will be healthy volunteers, it is anticipated that no contraindications, such as relevant medication use, will be present. However, if ondansetron is administered, participants will be closely monitored for both relief from nausea and potential side effects, including headache, dizziness, and other known reactions, for at least 1 hour following administration.

The decision to administer ondansetron will be documented, including the time of administration, the participant's reported nausea level, and any subsequent symptoms.

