8.2 Randomisation, blinding and treatment allocation

After confirming suitability for inclusion and obtaining written informed consent during the initial visit, participants will be scheduled for a second visit (referred to as the test day). Prior to this test day, an investigator will randomise the subjects in a 1:1 parallel fashion to receive either taVNS or sham stimulation. The randomisation of participants will be conducted using Castor, an electronic data capture system. The concealment list will be generated and provided to a co-worker in the same department as the coordinating investigator. For emergencies, drs. [name] will be provided with the concealment list and will be able to de-blind. The concealment list provides information on which participant will get active taVNS and who will get

sham stimulation. This information will remain confidential, and the concealment list will be sealed until after the initial analysis.

In this study, blinding procedures will be implemented. The tVNS device used will be identical for both the active and sham groups, and the ear electrodes will be placed at the same anatomical location. Furthermore, the device will blink in both groups to ensure that participants remain blinded to their treatment allocation. The key differences are that the sham group will receive a device with a non-conducting electrode, and that the electrodes for the taVNS and sham groups will be slightly different. As a result, the investigator responsible for programming the devices on the test day will be aware of treatment allocation. To maintain proper blinding for the initial analysis, the randomization code will be changed prior to the data analysis using Castor. The randomization code will be kept confidential until after the modified intention-to-treat analysis has been reported.

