8.3.2 Visit 2: Test day

Participants will arrive at the NUTRIM CRU at Maastricht University after an overnight fast. To account for the distinct circadian rhythms of the hormones being measured, the test day is scheduled between 9:00 a.m. and 12:00 p.m. This timing ensures that measurements are taken before the natural ghrelin peak, which typically occurs around noon, optimizing sensitivity to detect any effects of the intervention (61, 62). Although cortisol levels peak around 8:00 a.m. and are still in decline during this window, they are not yet at their most stable (62). However, this is deemed acceptable since cortisol is a secondary outcome. Additionally, this time frame helps minimize the required fasting duration for participants, enhancing both feasibility and comfort.

Upon arrival, all participants will complete a checklist to verify compliance with the test day regulations. These regulations include not eating for at least 6 hours before the test day and not consuming extremely spicy or fatty foods, as well as alcohol, on the day prior to the test day. On the day of the test, participants are only permitted to drink small amounts of water. Additionally, due to the cortisol sampling, participants must refrain from consuming caffeine or engaging in physical exertion on the day of the test day. Participants should also avoid brushing their teeth, chewing gum, or smoking for at least 1 hour before the test session begins.

Once compliance is confirmed, the coordinating investigator will prepare the tVNS device to ensure it is ready for immediate use after nausea induction. This preparation involves adjusting the stimulation current based on each participant's sensitivity, keeping it below the sensory threshold, with current intensities ranging from 0.25 to 10mA.

Following this, the investigator will place an intravenous cannula for blood collection to measure plasma levels of ghrelin and motilin at four different time points.

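### Re-coding the randomisation list does not make the trial double-blind: the investigator who programs the device knows the arm, and the protocol does not separate that role from the analyst or from the VAS readings

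*Protocol*

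**What the plan says.** Section 3 describes a "monocentric, prospective, double-blind, randomized, placebo-controlled interventional trial", and the Summary uses the same label. The same section then says that, because the electrodes differ slightly, "the investigator responsible for programming the devices will be aware of the treatment allocation, while participants will remain blinded". Section 8.2 repeats this for the day itself: "the investigator responsible for programming the devices on the test day will be aware of treatment allocation".

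The person concerned can be identified from the procedures. In Section 8.3.2, before induction starts, "the coordinating investigator will prepare the tVNS device to ensure it is ready for immediate use after nausea induction"; Section 3 gives the same order of events. Section 5.2.1 says that the feeding tube "will be manually inserted by the coordinating investigator". Section 12.1 has the same role keep the key linking subject IDs to people.

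The second level of blinding is claimed in Section 3: "To ensure double blinding, the randomization code will be altered prior to data analysis, ensuring that the investigator conducting the analysis will be blinded". Section 5.1.2 repeats the re-coding step, "ensuring that the investigator conducting the data analysis remains unaware of the treatment allocation", and Section 8.2 adds that the list stays sealed through the first analysis. The analyst is not identified further.

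On the outcome side, Section 8.3.4 asks participants to rate their own nausea and describes the questionnaires as completed in Castor. The plan has 14 ratings: one before infusion, one when it stops, six during stimulation and six after it.

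**The concern.** A double-blind label tells the reader that a second party, besides the participant, is kept from knowing the arm where that knowledge could affect the result. Here the second party is meant to be the analyst, and the only means is a change of labels after the data are in. That step comes too late to affect anything said or done during the session. It also hides nothing from someone who remembers which subject ID had which electrode.

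The stakes are those of a small trial with a subjective primary outcome. Randomisation and device set-up both precede the induction, so the operator may know the arm while the induction is running. Its success decides whether the participant is analysed at all. After that come 12 ratings at 5-minute intervals, for which the protocol names nobody who is kept blind. If the label stands, a publication would claim a protection that the written procedures do not secure.

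**Working it through.** **Setting the statements side by side**

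| Step | Who, according to the protocol | Knows the arm? |
|---|---|---|
| Programming the device on the test day (3, 5.1.2, 8.2) | The programming investigator | Yes, stated |
| Setting up the device before induction (3, 8.3.2) | The coordinating investigator | Yes, if set-up includes the programming, as the adjustment of current implies |
| Placing the tube (5.2.1) | The coordinating investigator | Same role |
| Supervising the induction ratings and stopping the infusion | Not assigned to a blinded person | Not stated |
| 12 ratings during and after stimulation (8.3.4) | Scored by the participant; nobody named as present | Participant: no. Staff: not stated |
| Analysis (3, 5.1.2) | An unnamed investigator | Intended: no. Not required to be someone other than the programmer |

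**What re-coding can do.** Case A: the analyst set up no test day. New arm labels then keep that person blind. Case B: the analyst set up test days. That person can link IDs to electrodes from memory, or through the ID key if they are the coordinating investigator, so new labels and a sealed list hide nothing. The protocol allows both cases. In neither does re-coding reach back to the session.

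**What the induction decides.** Under Section 5.2.1 the test day ends if a VAS of 50 is not reached after 1.5 hours. Under Section 10 the modified ITT set contains randomised participants who completed the induction and started the intervention. Membership is therefore settled after randomisation, at a step where the operator may already know the arm.

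**The plan's own figure.** Section 4.4 gives a difference of 25 mm, SD 21.5, two-sided alpha 0.05 and power 0.80. The normal approximation gives n = 2 × (1.960 + 0.842)² × (21.5/25)² = 11.6, so 12 per arm. The exact t-test gives 12.65, so 13 per arm and 26 in total, with power 0.812. The stated 26 is reproduced, and nothing is wrong with it.

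**Illustration of sensitivity.** The standard error of the arm difference is 21.5 × √(2/13) = 8.43 mm. Suppose there is no true effect and bedside influence shifts the difference by b mm. The two-sided rejection rate follows from the noncentral t distribution with 24 degrees of freedom and noncentrality b/8.43:

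| Assumed b (mm) | b/8.43 | Rejection rate |
|---|---|---|
| 0 | 0 | 0.050 |
| 2.5 | 0.30 | 0.059 |
| 5 | 0.59 | 0.088 |
| 7.5 | 0.89 | 0.137 |
| 10 | 1.19 | 0.207 |

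Every value of b is assumed. The planned primary analysis is a linear mixed model, so the t-test is only a simple stand-in.

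**The case against.** The best defence is that the protocol is open about its arrangements. It says that the programmer is unblinded, and it says what it means by double blinding: participant plus analyst. The primary outcome is the participant's own score, and the participant is the person shielded by the same device, the same ear site and blinking in both arms. Sections 3 and 5.1.2 use different descriptions for the programmer and the analyst, and other staff exist, including a co-worker who holds the list (8.2) and research nurses (10). If the analyst is a different person, re-coding can work.

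Much of this stands, and it rules out several stronger readings that a reader might infer:

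- **That there is no blinding at all.** Participant blinding is stated and described, and it matters most for a self-rated outcome.
- **That the analyst delivered the treatments.** No section says so. The gap is that nothing prevents it.
- **That the unblinded operator conducts the VAS readings.** The protocol does not say who is present. The documented tasks are set-up and tube placement.
- **That escape medication is left to an unblinded person's discretion.** Section 5.3 ties it to a VAS of 80 or higher. It also requires a record: "The decision to administer ondansetron will be documented, including the time of administration, the participant's reported nausea level, and any subsequent symptoms". It names no decision-maker, but the criterion is the participant's score.
- **That the choice of covariates is left open as needed.** In Section 10.1 that qualifier belongs to adjustment for baseline nausea; potential confounders are to be included.

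The defence does not rescue the claim that re-coding ensures double blinding. Disclosing that the programmer knows the arm does not separate the roles. Nor is this detail that can wait for an analysis plan, because who is blinded during the session is a design statement that the protocol itself makes.

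**Conclusion.** The point holds in a limited form. Participant blinding is described; the second blind is asserted but not secured. Re-coding protects the analysis only if the analyst set up no test day, which the protocol does not require. It gives no protection during the induction or the 12 later ratings. As written, the design is participant-blinded with an intended blinded analyst.

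The conclusion rests on the role statements alone and needs no assumption about bias. The size of any bias is unknown. Error rates of about 9% for a 5 mm shift and 21% for 10 mm show only how sensitive a comparison of 13 per arm would be; they are not evidence that such a shift occurs.

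A related matter should be reconciled separately, because participant blinding carries most of the weight. Sections 3 and 8.3.2 put the current below the sensory threshold, while Section 5.1.1 puts it above threshold.

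**What to change.** 1. In the Summary and Sections 3 and 8.2, describe the trial as participant-blinded with blinded analysis. Delete the claim that re-coding ensures double blinding.
2. State that the analyst is an existing member of the group who programmed no device and attended no test day, and that the analysis script is fixed before the arm codes are joined to the data.
3. Have participants enter every VAS score themselves in Castor, during the induction as well as afterwards, under a fixed neutral script and without comment from the operator. Section 8.3.4 already plans questionnaire completion in Castor, so this mainly extends and standardises it.

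The cost is protocol wording, the choice of a colleague as analyst and a short bedside script, with no extra visits or staff. The downside is a less favourable design label. No change to the rescue rule is proposed.

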4. STUDY POPULATION

4.1 Population

To investigate whether taVNS is effective in counterbalancing the nausea response induced by intragastric lipid infusion, healthy volunteers will be enrolled until 26 responders to nausea induction have completed the study. Participants will be recruited through various channels, including public advertisements and local newspapers. Both males and females aged between 18 to 65 years are eligible for inclusion.

4.2 Inclusion criteria

In order to be eligible to participate in this study, a subject must meet all of the following criteria:

- Healthy participants (defined as those without a pre-existing medical comorbidity).
- Aged between 18-65 years.
- Ability to understand and speak the Dutch language.
- BMI between 18 and 25 kg/m².

4.3 Exclusion criteria

A potential subject who meets any of the following criteria will be excluded from participation in this study:

- Medical history of chronic or severe diseases affecting the cardiovascular, respiratory, urogenital, gastrointestinal/hepatic, haematologic/immunologic, HEENT (head, ears, eyes, nose, throat), dermatological/connective tissue, musculoskeletal, metabolic/nutritional, endocrine, neurological/psychiatric systems.
- A history of major abdominal surgery.
- Gastrointestinal complaints.
- Any use of medication, especially those affecting gastric motility and nausea, apart from oral contraceptives.
- Current or lifetime psychopathology (including PHQ-9 and GAD-7 scores ≥ 10)
- Substance abuse, including excessive alcohol consumption (>20 alcoholic consumptions per week) and the use of recreational drugs.
- Smoking.
- Pregnancy, lactation, or intention to become pregnant during the study period
- Use of devices (e.g., cochlear implants) or other conditions (e.g. wounds, permanent ear-piercing) complicating the use of the tVNS device.

- Administration of investigational drugs or participation in any scientific intervention study that might interfere with this study (to be determined by the principal investigator) within 180 days preceding the commencement of the study.
- Students and employees of Maastricht University are not precluded from participation, unless they have a direct personal, professional or hierarchical position with regards to any of the study team members or their department.

